#### **6.1.1 Aim 1a) BMI-Z scores and DS – CMR factors**

---

To analyze this aim, the statistical model noted above will be modified to include an interaction term between DS and BMI-Z score for each CVD risk factor. An important interaction term will reflect varying association of BMI-Z by disease status. Based on preliminary data we estimate 50% of subjects with DS will have BMI $\geq$ 85%ile and undergo an OGTT. We will compare prevalence of IGT or IFG and T2DM between groups. (Although DS is associated with increased risk for T1DM, this would most likely present acutely and have already been diagnosed if present.)

**6.1.2 Aim 1b) DXA-measured FM** This sub aim will make use of the model in Aim 1a. Inclusion of FM in explaining CMR factors in the model should offset any statistical interaction between BMI-Z and DS status.

**Aim 1c) PWV [and LV Mass]** Using the model outlined previously, we will add PWV as an indicator of end organ damage to assess additional information provided by PWV, especially with regard to the interaction of BMI-Z and CVD risk factor levels. This approach will be used for CPP and LV mass as well.

**6.1.3 Aim 1d) Discrimination ability of BMI-Z and other screening measures** This analysis will be confined to children with DS, and will require for each CVD risk factor the determination before analysis of a threshold of high versus low, in order to evaluate discrimination. With BMI-Z, and each risk factor taken individually, we shall estimate the c-statistic, a measure of discrimination representing the area under the ROC curve of the tradeoff of sensitivity and specificity, for each screening measure as a predictor of high vs. low risk. Finally, we shall compare the additional discriminatory power of adding one screening measure to an existing screening measure, such as WC to BMI-Z to determine whether an additional screen is worth the expense and time. These contrasts will be implemented using the methods outlined by Pepe and colleagues.

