**Study Objective(s)**

**Part 1:**

**Primary**

**To compare the relationship between BMI-Z score and cardiometabolic risk factors in youth with DS, and in age-, sex-, race-, ethnicity-, and BMI-Z score-matched controls.**

- a) Compare cardiometabolic risk factors [non-HDL cholesterol, lipoprotein subclass particles, blood pressure, insulin resistance (measured by HOMA-IR), insulin sensitivity index (ISI), glucose tolerance, inflammatory markers, and adipokines)] in adolescents with DS and in matched controls.
- b) Determine the extent to which adiposity (fat mass by DXA) explains this relationship in DS vs. controls.
- c) Assess cardiac end organ injury (pulse wave velocity (PWV) and left ventricular mass) in relationship to BMI-Z score in adolescents with DS and controls. Determine whether BMI-Z or other measures of adiposity (skin-fold thickness, waist circumference) better discriminates adolescents with DS at increased cardiometabolic risk.

**Hypothesis:** DS is associated with worse cardiometabolic risk factors for a given BMI-Z compared to controls. This difference arises at least in part, from increased adiposity.

---

---

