### **2.1 Primary Aim 1**

The primary objective is to compare the relationship between BMI-Z score and cardiometabolic risk factors in youth with DS, and in age-, sex-, race-, ethnicity- and BMI-Z score- matched controls.

a) Compare cardiometabolic risk factors [non-HDL cholesterol, lipoprotein subclass particles, blood pressure, insulin resistance (measured by HOMA-IR), insulin sensitivity index (ISI), glucose tolerance, inflammatory markers, and adipokines)] in adolescents with DS and in matched controls.

b) Determine the extent to which adiposity (fat mass by DXA) explains this relationship in DS vs. controls.

---

c) Assess cardiac end organ injury (pulse wave velocity (PWV) and left ventricular mass) in relationship to BMI-Z score in adolescents with DS and controls. Determine whether BMI-Z or other measures of adiposity (skin-fold thickness, waist circumference) better discriminates adolescents with DS at increased cardiometabolic risk.

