Primary Aim: The primary aim is to compare the relationship between BMI-Z and cardiometabolic risk factors in youth with DS and matched controls. This relationship may be different in children with DS with and without CHD. In order to model the analyses appropriately, the primary outcome variables will be compared between children with DS with and without hemodynamically significant CHD. If the groups differ, subsequent analyses will include a dummy variable indicating presence/absence of hemodynamically significant CHD. Descriptive data analysis will summarize distributions of all risk factor measures (age, weight, BMI-Z, non-HDL-C, lipid levels, lipoprotein subclass particles, BP, HOMA-IR, ISI, inflammatory markers, adipokines, CPP, PWV, LV mass, gender, race, ethnicity, pubertal stage, pre-diabetes and diabetes status, physical activity). Subjects with DS will be compared to age-, sex-, race-, and BMI-Z matched controls, first by comparison of risk factor distributions by DS status. Next, we will fit separate regression models for each risk factor, with DS as the exposure of interest, adjusted for potential confounders, including pubertal stage, family history of CVD, dietary fat intake, and smoking history. Interaction terms among confounders will be used when data frequencies permit. Initial regressions will confirm the size and sign of associations of subject characteristics and CVD risk factors. Complementary analyses will implement propensity scores, using logistic regression to model DS as a function of observed covariates, and then will compare DS and non-DS children for each endpoint using weighted analyses. Weights will be calculated by the inverse of the fitted probability of DS. This method will standardize the comparisons of CVD risk factors by differences in observed characteristics of DS and non- DS children and thus will permit statements such as —If a sample of children otherwise comparable were alternatively DS and non-DS, what would be the differences in CVD risk factors? Finally, we will perform sensitivity analyses as to the potential impact on our results from unobserved potential confounders. Initial analyses will determine whether children with DS differ from their non-DS counterparts in terms of CVD risk factors and will become the basis for addressing the questions in the four sub-aims.

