## **6.2 Sample Size and Statistical Power**

Primary Aim: Assuming 155 evaluable children with DS and 105 evaluable children without DS for analysis and conservatively using nonparametric methods for comparison of CVD risk factors, power exceeds 0.85 to detect a between-group difference of 0.35 standard deviation (SD). For example, non-HDL-C is our primary CMR outcome measure, and 0.35 SD

---

corresponds to a difference of 7 mg/dl. A difference of 10 mg/dl is considered clinically relevant by pediatric cardiologists.

Secondary Aim: Power for the paired design can be assessed by assuming paired comparisons of residuals of a regression of BMI-Z on QOL and body image measures. Assuming that the outcomes, and thus residuals, will be continuous, power = 0.86 to detect as significant as little as 0.25 SD in differences between DS children and controls using nonparametric tests (Wilcoxon) that would be suitable for both continuous and ordered data. Thus, the sample should have substantial power to demonstrate even small differences between DS and matched controls.

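### Section 6.2 gives primary-aim power only for a group difference, not for the DS × BMI-Z interaction that Section 6.1.1 uses to compare relationships

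*Combined protocol and SAP*

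**What the plan says.** Section 2.1 sets the aim: "The primary objective is to compare the relationship between BMI-Z score and cardiometabolic risk factors in youth with DS", with matched controls as the comparison. Section 6.1 repeats it for the analysis: "The primary aim is to compare the relationship between BMI-Z and cardiometabolic risk factors in youth with DS and matched controls". Sub-aim (a) in Section 2.1 is worded differently, as a comparison of the risk factors themselves between the two groups. The hypothesis in the Protocol Synopsis is also about level: "DS is associated with worse cardiometabolic risk factors for a given BMI-Z compared to controls". Its second sentence attributes the difference, at least in part, to greater adiposity.

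Section 6.1 begins with group comparisons and regressions on DS status. Section 6.1.1 then modifies the model for Aim 1a to "include an interaction term between DS and BMI-Z score for each CVD risk factor". Section 6.1.2 (Aim 1b) adds DXA fat mass to that model and expects it to cancel any such interaction.

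The only power statement for the primary aim, in Section 6.2, is "power exceeds 0.85 to detect a between-group difference of 0.35 standard deviation (SD", obtained by "conservatively using nonparametric methods for comparison of CVD risk factors". It gives no slope difference, BMI-Z spread, alpha or sidedness. Section 6.3 says that, if the groups do not differ, confidence bounds will be used to exclude clinically important differences.

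**The concern.** A comparison of relationships is a comparison of slopes. The power quoted for the primary aim is for a different quantity, an unadjusted difference in level. A reader of Section 6.2 could take the figure above 0.85 to cover the Aim 1a test, which it does not. Without a detectable slope difference or an expected interval width, nobody can say in advance what a non-significant interaction would mean.

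Aim 1b inherits the problem. As written, Section 6.1.2 looks only at what fat mass does to the interaction. Suppose DS carries worse risk by a constant amount at every BMI-Z and adiposity accounts for it. That is what the hypothesis says. The interaction would then be near zero before and after fat mass is added, and the described analysis would miss the explanation.

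**Working it through.** **Inputs from Section 6.2.** Sample: "Assuming 155 evaluable children with DS and 105 evaluable children without DS for analysis". Outcome: "non-HDL-C is our primary CMR outcome measure". A difference of 0.35 SD is said to equal 7 mg/dl, so the outcome SD is 7 / 0.35 = 20 mg/dl. A difference of 10 mg/dl is called clinically relevant.

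**Assumptions, not in the documents.** Alpha 0.05. BMI-Z SD of 1.0 in both groups, range 0.8 to 1.2. Residual SD equal to the outcome SD of 20 mg/dl.

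**Step 1: the plan's own figure.** In SD units, the standard error of the group difference is √(1/155 + 1/105) = 0.1264, and 0.35 / 0.1264 = 2.769. For the Wilcoxon test, multiply by √0.955, which gives 2.706.

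| Test | Two-sided 0.05 | One-sided 0.05 |
|---|---|---|
| Normal | Φ(2.769 − 1.960) = 0.79 | Φ(2.769 − 1.645) = 0.87 |
| Wilcoxon | Φ(2.706 − 1.960) = 0.77 | Φ(2.706 − 1.645) = 0.856 |
| Mann-Whitney, 10,000 simulations | 0.767 | 0.853 |

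At 155 and 105, the stated figure is reached only one-sided. A two-sided Wilcoxon test with 155 in each group would give 0.853, but that is not the planned sample.

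**Step 2: the interaction.** The standard error of the slope difference is (residual SD / BMI-Z SD) × √(1/155 + 1/105). With BMI-Z SD 1.0 it is 20 × 0.1264 = 2.53 mg/dl per BMI-Z unit.

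- Detectable with 80% power: (1.960 + 0.842) × 2.53 = 7.1 mg/dl per unit, or 0.354 SD per unit.
- 95% CI half-width: 1.96 × 2.53 = 4.95 mg/dl per unit.
- Power for a true slope difference d: Φ(d / SE − 1.960). For d = 5, 5 / 2.53 − 1.960 ≈ 0.02, so power is 0.51.

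| | BMI-Z SD 0.8 | 1.0 | 1.2 |
|---|---|---|---|
| Detectable at 80% power (mg/dl per unit) | 8.9 | 7.1 | 5.9 |
| 95% CI half-width (mg/dl per unit) | 6.2 | 5.0 | 4.1 |
| Power at 2 mg/dl per unit (0.10 SD) | 0.09 | 0.12 | 0.16 |
| Power at 4 (0.20 SD) | 0.24 | 0.35 | 0.48 |
| Power at 5 (0.25 SD) | 0.35 | 0.51 | 0.66 |
| Power at 7 (0.35 SD) | 0.60 | 0.79 | 0.91 |
| Power at 10 (0.50 SD) | 0.89 | 0.98 | >0.99 |

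Least-squares simulation at BMI-Z SD 1.0 (4,000 runs per point) agrees: 0.12, 0.34, 0.49 and 0.79 at 0.10, 0.20, 0.25 and 0.35 SD per unit.

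**Step 3: scale.** A slope difference of 5 mg/dl per unit moves the groups apart by 2 × 5 = 10 mg/dl over two BMI-Z units, the size Section 6.2 calls clinically relevant. Power for it is about one half. With BMI-Z SD 1.0, an estimate of exactly zero would have a 95% interval that only just excludes it.

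**Step 4: residual SD.** If covariates explained 10% or 20% of the variance, power at 0.25 SD per unit would rise from 0.51 to 0.55 or 0.60. Correlation between covariates and the interaction term would pull the other way.

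**The case against.** The strongest reply is that the stated power does serve the primary aim in part. Sub-aim (a) and the hypothesis are about levels, the controls are matched on BMI-Z, and Section 6.1 makes the initial group comparisons the basis for the sub-aims. This stands. The gap is an omission for the interaction, and it would be wrong to infer that the power statement is irrelevant to the whole aim.

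A reader might also infer that the study could hardly detect any difference in slope. The documents do not support that. They give no expected slope difference, and power is about 0.98 at 10 mg/dl per unit.

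Nor do they say that a non-significant interaction will be taken as equal slopes. Section 6.1.1 speaks of an important interaction rather than a significant one, and Section 6.3 plans to use confidence bounds. That softens the risk. But Section 6.3 refers to differences in risk factors between groups and sets no slope margin.

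Finally, it is tempting to say that a null interaction leaves Aim 1b with nothing to explain. The Aim 1a model contains a DS term, so the needed coefficient is available. Section 6.1.2 simply does not say that it will be examined.

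**Conclusion.** The point holds in a limited form. The power in Section 6.2 describes an unadjusted group difference and not the Aim 1a interaction. At 155 and 105 it is about 0.77 to 0.79 two-sided. Under the assumptions above, interaction power for non-HDL-C is low to moderate below about 0.35 SD (7.1 mg/dl) per BMI-Z unit and high for much larger differences. The 0.35 here is per BMI-Z unit. It resembles the 0.35 SD in Section 6.2 only because the two standard errors coincide when BMI-Z SD is 1. These sizes depend on a BMI-Z SD and residual SD that the sponsor has not stated.

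Separately, Section 6.1.2 does not test the level hypothesis that it is meant to explain. A reader might conclude that the DS main effect must become the sole confirmatory test. The documents do not require that; it is a design choice for the sponsor.

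**What to change.** - **Section 6.2:** state that the existing figure is for the unadjusted group difference, give its alpha and sidedness, and correct it. Relabelling it alone would keep a value reached only one-sided. Add the interaction's detectable slope difference or expected 95% CI half-width (about 5 mg/dl per BMI-Z unit under the assumptions here), with the sponsor's own BMI-Z SD and residual SD.
- **Section 6.1.1:** report the interaction as an estimate with a 95% CI, and say that non-significance will not be taken as equal slopes.
- **Section 6.1.2:** assess Aim 1b by the change in the BMI-Z-adjusted DS coefficient when fat mass is added, as well as by the change in the interaction. Take that coefficient from a model without the interaction, or centre BMI-Z, because otherwise it refers to BMI-Z of zero.

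The cost is a few sentences, with no new data or participants. The stated power will look less favourable.

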#### **4.1.1 Visit 1**

- Fasting Blood Sample: Will be completed by nursing staff. A total of approximately 12.5 mL (approximately 2½ teaspoons) of blood will be obtained from all participants. Subjects who do not undergo OGTT will be allowed to eat after the fasting blood sample.
- OGTT: A 2 hour OGTT will be done only in subjects with BMI  $\geq$ 85thtile, not known to have diabetes. A total of approximately 7.5 mL (1½ teaspoons) of blood will be obtained. The OGTT will be performed by nursing staff. A blood drawing IV will be placed. Baseline BG and insulin will be obtained. Subjects will ingest glucose solution (1.75 g/kg; maximum of 75 g) over 2 minutes. BG and insulin will be draw at 30, 60, 90, and 120 minutes via a blood drawing IV. For subjects refusing a blood drawing IV, BG and insulin will be drawn fasting and at 120 minutes. If a subject refuses the OGTT, only fasting labs will be obtained. Subjects who undergo OGTT will be allowed to eat after the OGTT is completed.
- Anthropometric Measurements: Performed by trained research anthropometrists, in order to assess body composition.

- 
- DXA Scan: The scan measures body composition and will be conducted and analyzed by trained staff.
  - Pubertal Status: Tanner staging of puberty will be performed by a pediatric endocrinologist team member. This exam will take place in a private exam room.
  - Pulse Wave Velocity (PWV) and Pulse Wave Analysis (PWA): The PWV and PWA will be performed by a trained technician
  - Echocardiography: Left ventricular mass will be measured by a trained sonographer and analyzed by the study cardiologist.
  - Family History of CVD, Dyslipidemia, T2DM: The study coordinator or appropriate member of the investigative team will administer a CRF to collect relevant patient medical history, family history of CVD/dyslipidemia/T2DM, sedentary and physical activity for each participant. Each question will be verbally communicated to the parent/participant, and the team member will show the questions as they are read, as appropriate.

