#### **5.1.8 Safety Evaluation**

The study investigators will be responsible for safety monitoring. A routine needle stick or an IV line used for drawing blood may cause some discomfort (topical anesthetic cream will be available), bruising, and rarely fainting. Use of the anesthetic cream may cause an allergic reaction. Although high adiposity is possible in participants with BMI < 85th percentile and might contribute to abnormal glucose tolerance, we will limit the subjects undergoing OGTT 1) to minimize participant burden in this cohort of children with developmental disabilities, and 2) on the likelihood of finding cardiometabolic abnormalities. We confined our IR assessment to HOMA-IR rather than IVGTT or clamp studies--considered the gold standard for IR assessment-- in the spirit of sensitivity to these children with intellectual disabilities and their families. We will obtain interim time points within the OGTT to calculate ISI, a measure of whole body insulin sensitivity. This requires a minimum of 5 time points, necessitating the placement of a blood-drawing IV. Given the children's developmental disabilities, some children may not tolerate this procedure—in this subset only time points 0 and 120 will be drawn and ISI omitted from their analyses.

Participants will be fasting 12 hours prior to their study visit. This may cause hunger pangs, upset stomach, headache, or light-headedness. If the participant shows any signs of clinical instability or definitively decides to discontinue participation, the study visit will be ended. Possible side effects of the OGTT include temporary high or low blood sugar. A risk of the OGTT includes an upset stomach. Participants will be monitored by a nurse or doctor during the study procedures. Episodes of low blood glucose will be treated with oral or IV glucose when indicated.

During the study visit, if a participant is found to have any previously unknown medical conditions, they will be referred to their pediatrician for care.

This protocol also involves exposure to radiation from the DXA scans. However, this involves a very small radiation exposure, which is unlikely to cause any untoward effects to the participant. Being that the protocol may be unsafe to an unborn child, pregnancy is an exclusion criterion of the study.

The noninvasive measures of arterial stiffness and central pulse pressure are done via Pulse Wave Velocity and Pulse Wave Analysis. This poses little risk to the patient.

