### 8.3.3 Risk Assessment

The risks of participating in this study are relatively small and the investigators believe the overall study is of minimal risk to the participants. An OGTT will only be administered to subjects that have BMIs  $\geq$  85th percentile, not known to have diabetes.

Expected risks to the subject are as follows:

- Blood draw may result in temporary discomfort from the needle stick, bruising, fainting, weakness, and rarely an infection at the site
- Possible side effects of the OGTT include temporary high or low blood sugar and upset stomach
- Anthropometric measurements and pubertal status exam poses minimal risks
- Exposure to radiation during DXA scan
- Sharing of private health information (PHI) including dietary intake, demographic information, health history and medical information
- Pulse wave velocity and pulse wave analysis poses minimal risks
- 12 hour overnight fasting may cause hunger pangs, upset stomach, headache, or lightheadedness
- Blood pressure measurement by auscultation may cause temporary numbness/tingling in the arm
- SenseWear® Armbands worn for 7 consecutive days may cause skin irritability
- Sensitive psychosocial issues may arise during questionnaire assessment

A small amount of blood (about 3 teaspoons) will be drawn at major assessment points. Adolescents may experience some degree of discomfort, bruising, or lightheadedness with fasting blood draws. There is also a risk of infection when blood is drawn. These occurrences are rare, generally mild, and respond to conservative treatment.

The OGTT is frequently used to screen for diabetes and impairments in glucose regulation in children both within the confines of a study and in routine clinical practice; additional intermediate blood draws will be performed for glucose and insulin in order to assess insulin sensitivity. Because of these intermediate time points for blood collection, an intravenous line will be placed, which can be associated with discomfort and a small risk of infection. The use of EMLA cream is optional to minimize discomfort to the study participant. Experienced pediatric research nurses will perform the OGTT; OGTT are routinely performed in this setting. Seven blood samples are required and the volumes of blood will be minimized to reduce the risk of anemia. The concern with OGTT is hypoglycemia occurring 2-3 hours after consumption of the dextrose load. If hypoglycemic

---

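### IGT and ISI are seen only in children with BMI at or above the 85th percentile who have an OGTT, yet Aim 1d judges BMI-Z on every risk factor and Aim 1a pools IGT with IFG, with no denominator given

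*Combined protocol and SAP*

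**What the plan says.** **Who is tested.** Section 8.3.3 states the restriction: "An OGTT will only be administered to subjects that have BMIs" at or above the 85th percentile, and who are not known to have diabetes. Table 1 and sections 4.1 and 4.1.1 agree. Section 4.1.1 adds: "If a subject refuses the OGTT, only fasting labs will be obtained". A child who refuses only the blood-drawing IV still drinks the glucose and is sampled at 0 and 120 minutes. For such children section 5.1.8 says "in this subset only time points 0 and 120 will be drawn and ISI omitted from their analyses". Known T2DM is not an exclusion.

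**Who has fasting measures.** Table 1 and section 5.1.3 plan fasting glucose, insulin, lipids and HbA1c for all subjects.

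**What is analysed.** Glucose tolerance and ISI are among the risk factors listed in section 2.1: "insulin sensitivity index (ISI), glucose tolerance, inflammatory markers, and adipokines)] in adolescents with DS and in matched controls". Section 6.1.1 says "Based on preliminary data we estimate 50% of subjects with DS will have BMI" at or above the 85th percentile and so undergo an OGTT, and then: "We will compare prevalence of IGT or IFG and T2DM between groups". Section 6.1.3 (Aim 1d), in DS only, requires "for each CVD risk factor the determination before analysis of a threshold of high versus low". It then estimates a c-statistic for each screening measure and the gain from adding one screen to another, such as waist circumference to BMI-Z. It makes no exception for OGTT-derived factors.

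**The concern.** Two outcomes observed in different sets of children are joined in one prevalence. IFG can be classified in everyone with a fasting sample. IGT can be classified only in OGTT completers above a BMI cut-off. The plan does not say whether untested children are left out, treated as missing or counted as normal.

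Aim 1d is the more serious part. Whether IGT or ISI is observed depends on BMI, and BMI-Z is one of the measures under evaluation. Selecting on the predictor changes its c-statistic and its contrast with waist circumference or skinfolds. Section 6.1.3 uses that contrast to decide whether an extra screen is worthwhile, and section 8.3.5 says the results will tell primary care which measure to use. For IGT and ISI, an unstated coding choice could decide the answer.

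**Working it through.** **Inputs from the documents.** 155 DS and 105 controls (section 6.2); 50% of DS at or above the 85th percentile (section 6.1.1). The plan gives no IGT rate, OGTT uptake, c-statistic or power for IGT, so there is no figure of its own to reproduce. The control share is not stated; 50% is assumed because controls are matched on BMI-Z. Expected numbers eligible for testing are 0.5 × 155 ≈ 78 DS and 0.5 × 105 ≈ 52 controls.

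**Step 1. Who contributes to what.**

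| Outcome | Observed in |
|---|---|
| IFG, HbA1c, HOMA-IR, non-HDL-C | all with a fasting sample |
| IGT | BMI ≥ 85th percentile, no known diabetes, OGTT done (two samples suffice) |
| ISI | as IGT, and all five time points drawn |

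**Step 2. Aim 1d.** Simulation of 400,000 children. Assumptions: BMI-Z and a rival measure each correlate 0.4 with latent 2-hour glucose, the top 15% are IGT, and testing is done only above the BMI-Z median (the 50% share). The two measures are equally good by construction. Each cell gives the c-statistic for BMI-Z / rival.

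| Correlation between measures | All children tested | Untested counted as normal | Tested only |
|---|---|---|---|
| 0.5 | 0.71 / 0.70 | 0.84 / 0.75 | 0.63 / 0.65 |
| 0.7 | 0.71 / 0.70 | 0.84 / 0.78 | 0.63 / 0.64 |
| 0.9 | 0.71 / 0.71 | 0.84 / 0.82 | 0.62 / 0.63 |

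About 25% of true IGT cases are never tested.

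The null case has a closed form. Suppose BMI-Z is unrelated to IGT, prevalence is 15%, and untested children count as normal. Recorded cases are then 7.5% of children, all in the upper half. Recorded non-cases are 50% (lower half) plus 42.5% (upper half). The c-statistic is (0.50 × 1 + 0.425 × 0.5) / 0.925 = 0.77, where the true value is 0.50.

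Range: a second simulation varied the BMI-Z correlation from 0.2 to 0.5 and prevalence from 10% to 20%, with waist circumference slightly better than BMI-Z. The BMI-Z c-statistic was 0.60 to 0.77 with all tested, 0.56 to 0.68 tested only, and 0.80 to 0.86 with untested as normal. The gain of waist circumference over BMI-Z was about +0.025, +0.036 to +0.043, and −0.033 to 0.000 respectively.

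**Step 3. Between-group IGT.** Let p_hi and p_lo be the IGT rates above and below the cut-off and u the uptake. True prevalence = 0.5·p_hi + 0.5·p_lo; prevalence over all subjects with untested as normal = 0.5·u·p_hi; completers only = p_hi, if refusal is unrelated to glucose status. All rates are assumed; each cell is DS vs control.

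| Scenario | True | Over all subjects | Completers |
|---|---|---|---|
| 20%/10% in both, full uptake | 15% vs 15% | 10% vs 10% | 20% vs 20% |
| 20%/10% in both, uptake 80% vs 100% | 15% vs 15% | 8% vs 10% | 20% vs 20% |
| DS 15%/15%, controls 15%/5%, full uptake | 15% vs 10% | 7.5% vs 7.5% | 15% vs 15% |

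Pooling with IFG dilutes the second row. With IFG at an assumed 10% in both groups, independent of IGT, the composite is 1 − 0.92 × 0.90 = 17.2% vs 1 − 0.90 × 0.90 = 19.0%.

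**The case against.** The restriction is disclosed and justified by participant burden and low expected yield (sections 5.1.8, 6.3 and 8.3.3), and ISI is explicitly dropped for children with a two-sample test. The OGTT rule is the same in both groups, which are matched on BMI-Z. The prevalence sentence directly follows the estimate of how many DS subjects will have an OGTT, so a tested-only denominator is a natural reading. On that reading the group comparison is valid for its stratum. T2DM is named separately, so counting known cases may already be intended. All of this stands, and it limits the prevalence part to a missing denominator.

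A reader might infer that OGTT refusal is more likely in DS, so that IGT prevalence is understated more there. The documents do not say so. Section 5.1.4 links developmental delay to not tolerating the IV, and those children keep the 120-minute sample. Outright refusal, in section 4.1.1, is not tied to either group.

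It can also be said that the large Aim 1d distortion requires untested children to be coded as normal, which no section states. That is correct. Among tested children the contrast between measures moves little: about 0.02 at a correlation of 0.5, and less than 0.01 at 0.9. But the BMI-Z c-statistic itself still falls from about 0.71 to 0.63, so the tested-only handling does not give a value for the whole DS group either.

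**Conclusion.** The point holds for OGTT-derived outcomes. Followed as written, Aim 1d yields BMI-Z c-statistics for IGT and ISI that do not describe the DS group under either handling: too high if untested children count as normal (about 0.84 against 0.71), too low among tested children (about 0.63). The first handling can also cancel or reverse the sign of a contrast with another measure. These sizes rest on assumed correlations and prevalence; the directions held throughout the range tried.

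A reader might conclude that the between-group prevalence comparison is biased outright, or that discrimination is distorted for every risk factor. Neither is supported. The prevalence contrast is biased only if all subjects form the denominator and uptake, or IGT below the 85th percentile, differs by group. Among completers it is valid for that stratum unless refusal is related to glucose status. Non-HDL-C, the primary outcome, and blood pressure, HOMA-IR, fasting glucose, HbA1c, inflammatory markers, PWV and LV mass are planned in all subjects and are untouched.

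**What to change.** **Section 6.1.3 (Aim 1d).** Base the contrasts of BMI-Z with other measures on factors measured across the full BMI range: non-HDL-C, blood pressure, fasting glucose, HbA1c, HOMA-IR, PWV and LV mass. Report c-statistics for IGT and ISI only as conditional on BMI at or above the 85th percentile and a completed test, or omit them. State that untested children are never counted as normal.

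**Section 6.1.1 (Aim 1a).** Replace the pooled sentence with three comparisons:
- IFG and HbA1c in all subjects with a fasting sample;
- IGT among OGTT completers, adjusted for BMI-Z, with completion reported by group;
- T2DM as known plus newly found cases, stating the criterion for new cases, since the 2-hour criterion applies only to completers.

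**Cost.** Wording only; no additional OGTTs or visits. The IGT interval is wider. With an assumed 15% in both groups, the 95% half-width for the difference is 1.96 × √(0.15 × 0.85 × (1/155 + 1/105)) = 8.8 points on the full sample and 1.96 × √(0.15 × 0.85 × (1/78 + 1/52)) = 12.5 points among those eligible for testing at full uptake. Power for an assumed 20% vs 10% in that stratum is about 0.32 (two-sided 5%), so the IGT comparison should be presented as estimation. No IGT information is lost, because untested children contribute none.
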